Eligible subjects identified from the medical record will be those who are 1) scheduled to undergo RALPN surgery, 2) willing to consent to the surgery being performed by one of the four surgeons participating in the study, and 3) willing to be assigned by randomization to a preparation method (VR-aided or control). Each case will be assigned to one of the two preparation methods by a randomization procedure that is stratified by surgeon (four separate surgeon-specific randomization schedules.) Each surgeon-specific randomization schedule will be prepared using permuted blocks of size 2; i.e., each 2-patient block will be some permutation of {VR-aided, Control}. Thus, each surgeon’s cases will be randomized in a 1:1 ratio. Use of permuted blocks thus avoids any confounding of preparation method with temporal trends (e.g., trend due to a learning curve.) Approximately 20 sequentially numbered opaque sealed envelopes (SNOSEs) will be prepared for each individual surgeon, each containing the treatment assignment for one case, and will provided to the Research Coordinator. The treatment code will remain concealed inside the envelope until

the moment the case is ready to be prepared. Patients, personnel gathering data from the video review, and statistician will be blinded. Control and intervention groups identifiers will be known only to the research personnel opening the sealed envelope for random group assignment and extracting patient data from the electronic medical record.

We calculated the sample size based on our pilot data of the total operative time, which shows an effect size of 0.44 regarding the difference of total operative time between VR-aided and control groups. We took the within-surgeon correlation to be 0.3. We use data from the most-of-interest variable (aka total operative time). To account for the within-cluster correlation, we adopted the sample size calculation method proposed in [1]. We took three values of within-cluster correction ($\rho = 0.3, 0.5, 0.7$) to consider low/moderate/high levels of within cluster correlation. In order to account for multiple endpoints and some other unpredictable factors, we propose to raise the sample size by 15%. We selected $\rho=0.3$ given the wide variation in case complexity seen in our pilot study, which drastically limited within-cluster clustering. Our target sample size using this method is 78 patients.

	$\rho = 0.3$	$\rho = 0.5$	$\rho = 0.7$
Before adjustment	34	39	47

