After 15% adjustment	39	45	54

[1] Diggle, P. J., Heagerty, P., Liang, K. Y., and Zeger, S. L. (2002). Analysis of Longitudinal Data. New York: Oxford University Press.

e. Statistical Model

Baseline values (means, standard deviations and proportions) will be tabulated together with corresponding confidence intervals (CIs) for each primary endpoint in both the Control Cases and Intervention Cases based on relevant historical data. For primary endpoints of various operative times, the nonparametric Wilcoxon signed rank test will be utilized to calculate the sample size needed to have 70% power to detect a 10% difference. False Discovery Rate (FDR) control will be enforced by using Benjamini-Hochberg procedure at the level of 5% in order to account for multiple testing issue.

Statistical analysis will include standard comparison of baseline endpoints between VR-aided and control groups with the appropriate statistical tests depending on the type of outcomes. For continuous outcomes (e.g. various operative times), the nonparametric Wilcoxon signed rank test will be used for comparison, which does not rely on the normality assumption. For binary outcomes (e.g. Mortality), Fisher's exact test will be used. P-values of all tests will be reported. The threshold of rejecting null hypothesis will be chosen at the conventional level of 0.05. Tests fail to be rejected will be reported as inconclusive. To study the adjusted difference between case/control group, we will also use generalized linear mixed model to regress the endpoint variables on Surgical and Clinical covariates listed in **Exhibit A**, where random effects will be imposed on surgeon clusters. Depending on the type of outcome, the linear mixed model (for continuous outcome) or the logistic mixed model (for binary outcome) will be used. To ensure normality, the continuous outcome will be Box-Cox transformed. In the regression analysis, we also use model diagnosis tools, such as QQ-plots to ensure various assumptions for the regression model are met. In

addition, to test the reliability of our model, we will also perform sensitivity analyses by splitting data into training and test set and perturb various assumptions (such as normality assumption and the Box-Cox transformation) in the regression model and inspect how well the results can be reproduced. The repeated measure ANCOVA will be used to test the adjusted difference between case/control groups.

V. SURGEON SURVEYS

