 - i. Identify upcoming cases for which VR models will be created.
 - ii. Oversee receipt of informed consents from all patients participating in the study.
 - iii. Provide the mobile phone used for viewing the VR models (Ceevra to provide VR headsets, 1 per surgeon user).
 - iv. Before each Intervention Case operation, review the source CT/MRI and then review the associated VR Model for purposes of case planning.
 - v. Participate in Post-Operative Surveys and Surgeon Experience Surveys.

VII. PROJECT IMPLEMENTATION

- a. **Protocol for Case Data.** Control Case Data and Intervention Case Data will be extracted from the EHR system, and the Post-Operative Surveys. It will be tracked via two forms maintained within REDCap which requires unique user IDs and passwords:
 - i. First form will include patient information (listed below) and a unique identifier. This form will be accessible by researchers only.
 - 1. Medical Record Number (MRN)
 - 2. Surgeon Number
 - 3. CT/MRI ID #
 - 4. Operation Date
 - 5. Unique Identifier
 - ii. Second form will include the unique identifier and outcomes data, but no PHI. See **Exhibit C** for example of data fields (partial nephrectomy cases). This form will be accessible by both site and Ceevra researchers.
- b. **Protocol for Control and Intervention Cases and Randomization**
 - i. For Intervention Cases, surgeons will be provided with the VR model to view prior to the operation in addition to the CT or MRI scan as described below. For Intervention Cases, surgeons will also have the option to view the VR model during the operation in addition to the CT or MRI scan. For Control Cases, surgeons will view the CT or MRI scan only.
 - ii. Subjects will be identified from the medical record as scheduled to undergo one of the surgery types being included in the study, with the surgery being performed by one of the surgeons participating in the study. Subjects will be randomized at a 1:1 ratio to either control or intervention groups using block randomization.
- c. **Protocol for VR Models**
 - i. PI/RC identifies upcoming Intervention Cases, based on the above criteria and the results of randomization, for which VR models are to be created.
 - ii. PI/RC obtains source CT/MRI for such cases, deidentifies the same using deidentifying software (or ensures that Radiology deidentifies the image prior to delivery to the PI/RC), delivers it to Ceevra along with a unique identifier.

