- iii. Ceevra creates VR model from the deidentified CT/MRI. Once completed:
 - Delivers VR Model back to PI/RC, along with the unique identifier.
 - Notifies applicable surgeon user (with copy to PI and RC) that VR Model is available for viewing through the mobile app.
- iv. Prior to operation for Intervention Cases, PI/RC contacts applicable surgeon user to ensure viewing of both the VR Model and the underlying CT/MRI.

d. Data Management Plan. Information regarding the Intervention Cases and Control Cases will be collected and analyzed, as detailed below. PHI will be reviewed during the study as necessary to identify potential participants with specified medical conditions, and a separate HIPAA authorization form will be obtained from patients. However, no PHI will be shared outside of the site.

- i. *Medical Images:* CTs and MRIs will be obtained from the hospital PACS system. All PHI will be removed from the images prior to sharing them with Ceevra.
- ii. *Case Data:* Intervention Case Data and Control Case Data will be extracted from the electronic video data, the hospital EMR system, and surgeon surveys to be administered following the operations. The case data will be tracked via the REDCap forms described above in Section VIII(b). The case data from the hospital EMR system will be entered into the applicable form by a researcher (other than the PI), and the results of the surgeon surveys may be entered into the applicable form either by a Ceevra researcher or a researcher (other than the PI).
- iii. *Data Quality.* REDCap forms will be configured to validate data fields at the time of entry to ensure the completeness and validity of data. REDCap locking and signing features will be employed to ensure record-level completeness.
- iv. *Data Security and Integrity.* REDCap employs secure authentication features to prevent unauthorized access to trial data. REDCap authorization features will be employed to ensure that form and data access is limited to the personnel with a need to access them. Additionally, REDCap data management mitigates the possibility of lost or corrupt data. REDCap audit trails provide the ability to verify the above, if needed.
- v. *Data Management and Data Computations.* Data management will be overseen by the RC. Data computations will be performed by the Biostatistician.

VIII. TRAINING, MEASURING & COMMUNICATING

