- a. Training with surgeon users on accessing/using mobile app and VR Models. Each surgeon will be trained either in person or via video call. During the training, the surgeon will be trained how to access the VR models from their mobile phones and how utilize several viewing features such as showing/hiding anatomical parts; zooming in/out on the model; and viewing the model in VR mode.
- b. Kickoff Meeting (in-person meeting at medical center):
 - i. Introduce participants
 - ii. Outline study processes, timeline and objectives
- c. Bi-Weekly Assessments
 - i. Data for cases involving the VR Models will be reviewed in a bi-weekly basis to assess whether there are any more or different issues in cases in which the VR Models were used during preoperative planning and, if so, whether any such differences can be attributed to the VR Models.
 - ii. In the event any unexpected adverse event occurs in a case in which a VR Model is used, the study will be immediately suspended until a determination is made whether such event is attributable to the VR Model. If such determination is affirmative, then the researchers will assess whether to continue or discontinue the study based on a number of factors including but not limited to the magnitude of the adverse event, the feasibility of preventative measures, and the likelihood of its recurrence after implementation of any such measures.
- d. Surgeon Experience Surveys (2x during study per surgeon)
- e. Study Conclusion Meeting (in-person): Final study results

EXHIBIT A
COVARIATES, ENDPOINTS AND SAMPLE SIZE BY SURGERY TYPE

		Robotic Assisted Laparoscopic Partial Nephrectomy
Surgical Covariates		
	Unit	
Surgeon Experience Level	Years	✓
Surgeon Identifier	Number	✓
Resident Involvement	Yes/No	✓
Fellow Involvement	Yes/No	✓
Clinical Covariates		
	Unit	
Age	Years	✓
Sex	M/F	✓
Charlson Comorbidity Index	NA	✓
Nephrometry Score	NA	✓
Mass Size	CM	✓
Mass Location	Segment	
Laterality	R/L	✓
Primary Endpoints		
	Unit	
Hilum Dissection	Minutes	✓
Hepatic Vessel Dissection	Minutes	
Tumor Localization	Minutes	✓
Tumor Resection	Minutes	✓
Reconstruction Time	Minutes	✓
Total Operative Time	Minutes	✓
Secondary Endpoints		
	Unit	
Blood Loss	cc	✓
Clamp Time	Minutes	✓
Warm Ischemia Time	Minutes	
Pringle Time	Minutes	
Conversion to Open	Yes/No	✓
Conversion to Radical	Yes/No	✓
Conversion from Wedge to Glissonian	Yes/No	
Intraoperative Complication	Yes/No	✓
Mortality	Yes/No	✓
Patient Hospital Stay	Days (post-op)	✓
Positive Margin	Yes/No	✓

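### The adjusted model includes resident and fellow involvement, which the plan does not fix before allocation; if involvement depends on arm, the adjusted difference is not the total effect of VR

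*Combined protocol and SAP*

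**What the plan says.** Section IV.e first plans comparisons without covariates: a Wilcoxon test for continuous outcomes and Fisher's exact test for binary ones. For the adjusted comparison it adds that "we will also use generalized linear mixed model to regress the endpoint variables on Surgical and Clinical covariates listed in" Exhibit A, with a random effect for surgeon. It closes with a second adjusted test: "The repeated measure ANCOVA will be used to test the adjusted difference between case/control groups". The covariates of that test are not restated; I read them as the same list.

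Under Surgical Covariates, Exhibit A ticks "Resident Involvement" and "Fellow Involvement" for partial nephrectomy, each as Yes/No. It does not say whether planned or actual involvement is meant.

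On timing, Section IV.d says "The treatment code will remain concealed inside the envelope until" the case is about to be prepared. On blinding, it says "Patients, personnel gathering data from the video review, and statistician will be blinded". Surgeons are not in that list.

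**The concern.** Randomisation protects an adjusted comparison when every covariate was settled before allocation. Whether a resident or fellow took part is, on its natural reading, a feature of the operation, and the operation comes after the envelope is opened. If knowing the arm, or having seen the VR model, alters who takes part, two things can go wrong:

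- Part of the VR effect may run through trainee involvement. Holding involvement constant then removes that part, so the model estimates a direct effect and not the total effect.
- If unmeasured case difficulty also influences involvement, conditioning on involvement makes the arms differ in difficulty, and the estimate is biased even when VR does nothing.

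Section IV.e does not say whether the unadjusted or the adjusted result governs if they disagree, so a distorted adjusted result could carry weight in the report.

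**Working it through.** **1. What the text establishes.** The plan states no figure on this point, so the first check is textual.

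- Both trainee items are in the model (Section IV.e with Exhibit A).
- The surgeon knows the arm before operating. Section VI.c requires the surgeon, in these words: "Before each Intervention Case operation, review the source CT/MRI and then review the associated VR Model for purposes of case planning". Section VII.c has the technology provider do the following: "Notifies applicable surgeon user (with copy to PI and RC) that VR Model is available for viewing through the mobile app". Section IV.d also confines knowledge of the group to certain research personnel, which cannot hold for the operating surgeon.
- Allocation precedes the operation (Section IV.d).
- No section fixes or records planned trainee involvement before the envelope is opened, names who decides it, or limits the model to pre-allocation covariates. The example data fields in Exhibit C do not list the two items.
- The other ticked covariates (surgeon identifier and experience, age, sex, Charlson index, nephrometry score, mass size, laterality) are baseline in nature.

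**2. Total versus direct effect.** If R is involvement, the gap is (change in the rate of R caused by VR) × (effect of R on the outcome). The documents give neither input. Assuming 10 to 30 percentage points and 0.25 to 0.75 SD:

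- 0.10 × 0.25 = 0.025 SD, and 0.025 / 0.44 = 6% of the design effect in Section IV.d
- 0.20 × 0.50 = 0.10 SD, or 23%
- 0.30 × 0.75 = 0.225 SD, or 51%

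This is a difference between two estimands. It does not measure bias from unmeasured difficulty.

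**3. Bias from unmeasured difficulty.** Illustrative simulation: 39 per arm and four surgeons (Sections IV.d and Exhibit A), two-sided 0.05, 4,000 replicates, and a linear model with surgeon terms standing in for the mixed model. The outcome in SD units is Y = τT + bR + cU + e, where T is arm, U is unmeasured difficulty, and cU + e has variance 1. Involvement follows logit P(R = 1) = g0 + gT·T + gU·U. All of these coefficients are assumptions.

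| Setting | τ, b, c | g0, gT, gU | R control / VR | Without R: estimate, rejection | With R: estimate, rejection |
|---|---|---|---|---|---|
| 1. R independent of arm | 0, 0.4, 0.5 | 0, 0, −1 | 50% / 50% | 0.00, 4.8% | 0.00, 5.1% |
| 2. No true effect | 0, 0, 0.5 | 0, 1, −1 | 50% / 70% | 0.01, 4.9% | 0.09, 7.0% |
| 3. Stronger dependence | 0, 0, 0.7 | −0.5, 1.5, −1.5 | 41% / 67% | 0.00, 5.6% | 0.20, 15.0% |
| 4. Strongest | 0, 0, 0.7 | −1, 2, −1.5 | 33% / 67% | 0.00, 5.4% | 0.26, 20.4% |
| 5. Mediator only | −0.44, 0.4, 0.5 | 0, 1, 0 | 50% / 73% | −0.35, 32.1% | −0.44, 45.1% |
| 6. Mediator and difficulty | −0.44, 0.4, 0.5 | 0, 1, −1 | 50% / 70% | −0.36, 36.5% | −0.36, 34.3% |

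In settings 1 to 4 rejection is type I error; in 5 and 6 it is power.

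Setting 5 agrees with step 2: −0.44 + 0.4 × (0.731 − 0.499) = −0.347, against −0.351 simulated without R. The adjusted model returns the direct effect and so shows more benefit than the total effect. In setting 6 the two distortions happen to cancel. In settings 2 to 4 harder cases were assumed to have less trainee involvement; reversing the sign of gU reverses the sign of the bias by symmetry. Neither size nor direction can be predicted from the plan.

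**4. What the trainee terms could be worth.** With an assumed 50% prevalence and an effect of d SD, R explains 0.5 × 0.5 × d² of the outcome variance. For d = 0.5 this is 0.0625 (6%); for d = 0.75 it is 0.141 (14%). On 78 patients that corresponds to 78 × 0.0625 = 4.9 and 78 × 0.141 = 11.0, or about 5 to 11 patients.

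**The case against.** The strongest reply is that the mechanism is not documented. No section says that the operating surgeon decides whether a trainee takes part, or that this can change after allocation. A rota may settle it, and setting 1 shows no harm then. A reader might infer that an unblinded surgeon will alter involvement; the documents are silent, and silence shows only that independence has not been secured.

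A reader might also infer that the plan itself predicts a change in delegation. It does not. Section I.b hypothesises better anatomical understanding leading to efficiency and recovery benefits. Confidence appears as something the surveys will assess (Section V.c and Exhibit B). Section I.d reports greater willingness to take on complex tumours, which concerns case choice. A change in how much a trainee does would also leave a Yes/No item unchanged if a trainee is present either way.

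The randomised comparison is already planned and listed first, and the mixed model is introduced as an addition, so readers will see both. Trainee involvement may be prognostic, and precision matters in a trial planned at 70% power.

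All of this stands as a limit on the claim. It does not remove the point: the plan adjusts for a variable that it neither defines as planned or actual nor fixes before allocation.

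**Conclusion.** The point holds conditionally. If resident or fellow involvement depends on arm, the mixed-model difference, and the ANCOVA difference if it uses the same covariates, does not estimate the total effect of VR. It is biased if unmeasured difficulty also drives involvement. If involvement is independent of arm, there is no bias.

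The documents give no size and no direction. The shifts of 0.09 to 0.26 SD, the type I error of 7% to 20%, and the 6% to 51% gap between total and direct effect all rest on assumed inputs. They should not be quoted as the expected error in this trial. In particular, the 51% figure needs both assumed extremes together.

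A reader might conclude that the trial's main comparison is compromised. The documents do not support that: the Wilcoxon and Fisher comparisons do not use these covariates. This is a cheap improvement to the adjusted analysis.

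**What to change.** In Section IV.e, limit the main adjusted model, and the ANCOVA likewise, to covariates fixed before the envelope is opened: age, sex, Charlson index, nephrometry score, mass size, laterality, and surgeon as already planned. Leave out actual resident and fellow involvement, or replace it with planned involvement recorded before the envelope is opened. Tabulate actual involvement by arm as a descriptive result, and show the model with the two trainee terms only as a sensitivity analysis. Whether surgeon should enter as a random or a fixed effect is a separate question on which nothing here bears.

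The cost is SAP wording plus, if planned involvement is used, one extra field completed before allocation. The downside is some loss of precision if involvement is prognostic and unrelated to arm: about 6% to 14% of outcome variance under the assumptions in step 4. Recording planned involvement recovers most of that, provided that it tracks what happens in theatre.

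### The trial randomises in within-surgeon pairs to guard against time trends, but the adjusted model has no case-order or block term and the signed-rank pairs are undefined: a near-free efficiency gain is left unclaimed

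*Combined protocol and SAP*

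**What the plan says.** Design (Section IV.d). Allocation is stratified by the four surgeons. "Each surgeon-specific randomization schedule will be prepared using permuted blocks of size 2", so each consecutive pair of one surgeon's cases holds one VR-aided and one control case. The stated reason is: "Use of permuted blocks thus avoids any confounding of preparation method with temporal trends (e.g., trend due to a learning curve". On numbering: "Approximately 20 sequentially numbered opaque sealed envelopes (SNOSEs) will be prepared for each individual surgeon". The target is 78 patients, 39 per arm.

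Analysis (Section IV.e and Exhibit A). Continuous outcomes are compared first by the Wilcoxon signed rank test. This is a paired test, and the plan does not say what its pairs are. For the adjusted difference, "we will also use generalized linear mixed model to regress the endpoint variables on Surgical and Clinical covariates listed in" Exhibit A, with random effects on surgeon. The listed covariates are surgeon experience in years, surgeon identifier, resident and fellow involvement, age, sex, Charlson index, nephrometry score, mass size and laterality. The item nearest to time is "Surgeon Experience Level", which separates surgeons but does not index successive cases by one surgeon. A repeated-measures ANCOVA is also named, without its terms.

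Data (Section VII.a). "Operation Date" is recorded on the first REDCap form, so case order within surgeon can be derived.

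**The concern.** When a design balances a prognostic factor, the treatment estimate varies less from trial to trial. A model that omits the factor does not see this. It leaves the factor's variance in the residual and reports a standard error larger than the true one. Here the balanced factor is position in each surgeon's sequence. If operative times drift over about 20 cases per surgeon, the adjusted tests of the five operative-time primary endpoints run below their nominal 5% and their confidence intervals are too wide. The trial is planned at only 70% power with false discovery rate control over several endpoints, so it has little precision to spare.

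The signed rank test raises a related question. Paired on the randomisation blocks, it removes a trend without any extra term. Paired in another way, or replaced in practice by an unpaired rank test because no pairs were specified, it would not.

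**Working it through.** **Inputs from the documents.** Blocks of 2 within four surgeons, 78 cases, effect size 0.44 and within-surgeon correlation 0.3 (IV.d); threshold 0.05 (IV.e).

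**Assumptions.** A two-sided test, since sidedness is not stated. Surgeons contribute 20/20/20/18 cases. The trend is linear and common to both arms. Its correlation r with the outcome within surgeon runs from 0 to 0.5, because the documents give no value.

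**The plan's own figure.** 34 × 1.15 = 39.1, taken as 39 per arm, and 2 × 39 = 78. This reproduces. The 34 itself depends on a cluster size that the plan does not state. Nothing below rests on it, and the power levels below are not a check of the 70% target; only the differences matter here.

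**Closed form.** Take the within-surgeon SD, trend included, as 1.

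- Reported SE without an order term: √(2/39) = 0.2265.
- True SE: about 0.2265 × √(1 − r²), because blocks of 2 cancel all but one step of the trend within each pair.
- SE ratio, reported to true: 1/√(1 − r²).
- True size without the term: 2Φ(−1.96/√(1 − r²)).
- 0.44/0.2265 = 1.943. Power with the term: Φ(1.943/√(1 − r²) − 1.96). Power without it: Φ((1.943 − 1.96)/√(1 − r²)), which stays at 49% for every r.

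At r = 0.3, √0.91 = 0.954. The SE ratio is 1.048, size is 2Φ(−2.055) = 4.0%, and power with the term is Φ(2.037 − 1.96) = 53%, against 49% without.

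**Simulation of the blocked design.** 20,000 trials per cell, models with arm and surgeon, without and with case order:

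| r | SE ratio (formula) | Size without / with | Power at 0.44 without / with | Points forgone |
|---|---|---|---|---|
| 0 | 1.00 | 4.8% / 4.8% | 48.3% / 48.3% | 0 |
| 0.2 | 1.02 | 4.6% / 5.0% | 48.4% / 50.2% | 2 |
| 0.3 | 1.05 | 4.1% / 5.2% | 48.1% / 51.8% | 4 |
| 0.4 | 1.09 | 3.2% / 5.1% | 47.6% / 54.8% | 7 |
| 0.5 | 1.15 | 2.0% / 4.9% | 47.3% / 59.9% | 13 |

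Repeat runs gave size without the term of 2.0% to 2.5% at r = 0.5 and about 4% at r = 0.3. If 0.44 is in total SDs, so that the within-surgeon effect is 0.44/√0.7 = 0.526, power without/with the term is 63.3%/67.0% at r = 0.3 and 64.0%/70.9% at r = 0.4: again about 4 and 7 points.

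**How large is each r?** Over 20 equally spaced cases the first-to-last range is 19/5.77 = 3.295 SDs of case position, so the fall is 3.295r within-surgeon SDs: 0.66 at r = 0.2, 0.99 at r = 0.3, 1.32 at r = 0.4 and 1.65 at r = 0.5. The last is 1.65/0.44 = 3.7 times the planned treatment effect.

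**Signed rank on the 39 blocks.** With no order term, size stays near 5%. At r = 0.5 power is 57%, against 47% for the model without order and 60% with it.

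**The case against.** Several objections have force.

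- **Trend size.** A reader might infer that the plan expects a learning curve, so that standard errors are too wide and power is lost as a matter of fact. The documents do not support this. The learning curve is a parenthetical example with no size, and at r = 0 nothing is lost. The loss must be stated conditionally.
- **What is lost.** With total variance held fixed, power without the term is flat at about 48%. The 0.44 comes from pilot data whose SD may already contain any trend. The points in the table are therefore precision that the design makes available and the model does not collect. If instead the trend is added to a fixed residual SD, power without the term does fall: from 49% to 46% for a first-to-last fall of 1 residual SD, but only by about 1 point for a fall of 0.5 SD.
- **r = 0.5 is extreme.** If 0.44 SD corresponds to the 10% target difference, it means operative time falling by about 3.7 × 10% = 37% within 20 cases. If 0.44 SD corresponds to the pilot's 30% reduction, it means about 112%, which is impossible.
- **The signed rank test.** A reader might infer that no analysis allows for order. The first-named test is paired, and the size-2 blocks are the only pairs the design creates. Paired that way it deals with the trend. What stands is that the plan does not say so. Nor can the repeated-measures ANCOVA be said to lack or to contain an order term, since its terms are unstated.
- **The simulated model is simpler than the planned one.** Nephrometry score, mass size and trainee involvement could absorb drift in case mix or staffing. If only VR-aided cases improve with time, the gain is smaller: about 1 point at r = 0.3 and 7 at r = 0.5.

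None of this supplies the missing term in the mixed model or defines the pairs.

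**Conclusion.** The gap is real and modest. The adjusted model ignores the ordering by which the trial randomises, and the signed-rank pairs are left open. Given a within-surgeon trend, the mixed model is conservative. Its estimate remains unbiased and its type I error stays at or below nominal, so a reader who concluded that the planned analysis is invalid would be going too far.

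The size depends on an assumed, linear trend common to both arms, and on a model with no other covariates. Under those assumptions, r = 0.2 to 0.4 is the range to weigh, with 2 to 7 points of power forgone. With covariates that track the trend, or a trend confined to one arm, the gain would be less. The change is worth making because it costs almost nothing, and because it has to be prespecified: adding case order after seeing results would be a data-dependent choice.

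**What to change.** 1. In Section IV.e and Exhibit A, add within-surgeon case sequence as a prespecified linear covariate in the mixed model for every continuous endpoint. Use the envelope number, or the order derived from the operation date, and say which. The envelope number is set before allocation and follows the order in which the blocks were built. Only the sequence number need enter the analysis file, not the date.
2. In Section IV.e, define the signed-rank pairs as the within-surgeon randomisation blocks of 2, and state how a block with only one analysable case is handled.

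Cost: a sentence or two in IV.e, one row in Exhibit A and one field in the analysis file. The covariate uses one degree of freedom, with no measurable power loss if there is no trend (48.3% with and without it at r = 0). Block pairing has one further cost: an incomplete block contributes no pair to the signed rank test.
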